
#### Inpatient, Any Diagnosis: ICD-10 Codes

D50.0 - Iron deficiency anemia secondary to blood loss (chronic)

- D62 Acute posthemorrhagic anemia
- 185.01 Esophageal varices with bleeding
- 185.11 Secondary esophageal varices with bleeding
- K20.0 Eosinophilic esophagitis
- K20.8 Other esophagitis

K22.11 - Ulcer of esophagus with bleeding

- K22.6 Gastro-esophageal laceration-hemorrhage syndrome
- K25.0 Acute gastric ulcer with hemorrhage
- K25.1 Acute gastric ulcer with perforation
- K25.2 Acute gastric ulcer with both hemorrhage and perforation
- K25.4 Chronic or unspecified gastric ulcer with hemorrhage
- K25.5 Chronic or unspecified gastric ulcer with perforation
- K26.1 Acute duodenal ulcer with perforation
- K26.2 Acute duodenal ulcer with both hemorrhage and perforation
- K26.4 Chronic or unspecified duodenal ulcer with hemorrhage
- K27.1 Acute peptic ulcer, site unspecified, with perforation
- K27.2 Acute peptic ulcer, site unspecified, with both hemorrhage and perforation
- K27.5 Chronic or unspecified peptic ulcer, site unspecified, with perforation
- K27.6 Chronic or unspecified peptic ulcer, site unspecified, with both hemorrhage and perforation
- K28.0 Acute gastrojejunal ulcer with hemorrhage
- K28.4 Chronic or unspecified gastrojejunal ulcer with hemorrhage
- K28.6 Chronic or unspecified gastrojejunal ulcer with both hemorrhage and perforation
- K29.01 Acute gastritis with bleeding
- K29.31 Chronic superficial gastritis with bleeding
- K29.41 Chronic atrophic gastritis with bleeding
- K29.51 Unspecified chronic gastritis with bleeding
- K29.71 Gastritis, unspecified, with bleeding
- K57.11 Diverticulosis of small intestine without perforation or abscess with bleeding
- K57.21 Diverticulitis of large intestine with perforation and abscess with bleeding
- K57.41 Diverticulitis of both small and large intestine with perforation and abscess with bleeding
- K57.51 Diverticulosis of both small and large intestine without perforation or abscess with bleeding
- K57.81 Diverticulitis of intestine, part unspecified, with perforation and abscess with bleeding
- K57.91 Diverticulosis of intestine, part unspecified, without perforation or abscess with bleeding
- K57.93 Diverticulitis of intestine, part unspecified, without perforation or abscess with bleeding
- K62.5 Hemorrhage of anus and rectum
- K64.0 First degree hemorrhoids
- K64.5 Perianal venous thrombosis
- K64.8 Other hemorrhoids
- K64.9 Unspecified hemorrhoids
- K92.0 Hematemesis
- K92.2 Gastrointestinal hemorrhage, unspecified
- N89.7 Hematocolpos
- N93.8 Other specified abnormal uterine and vaginal bleeding
- R04.2 Hemoptysis
- R31.0 Gross hematuria
- K20 Esophagitis
- K20.9 Esophagitis, unspecified
- K21.0 Gastro-esophageal reflux disease with esophagitis
- K25.6 Chronic or unspecified gastric ulcer with both hemorrhage and perforation
- K26.0 Acute duodenal ulcer with hemorrhage
- K26.5 Chronic or unspecified duodenal ulcer with perforation
- K26.6 Chronic or unspecified duodenal ulcer with both hemorrhage and perforation
- K27.0 Acute peptic ulcer, site unspecified, with hemorrhage

- K27.4 Chronic or unspecified peptic ulcer, site unspecified, with hemorrhage
- K28.1 Acute gastrojejunal ulcer with perforation
- K28.2 Acute gastrojejunal ulcer with both hemorrhage and perforation
- K28.5 Chronic or unspecified gastrojejunal ulcer with perforation
- K29.21 Alcoholic gastritis with bleeding
- K29.61 Other gastritis with bleeding
- K29.81 Duodenitis with bleeding
- K29.91 Gastroduodenitis, unspecified, with bleeding
- K31.811 Angiodysplasia of stomach and duodenum with bleeding
- K55.21 Angiodysplasia of colon with hemorrhage
- K57.01 Diverticulitis of small intestine with perforation and abscess with bleeding
- K57.31 Diverticulosis of large intestine without perforation or abscess with bleeding
- K57.53 Diverticulitis of both small and large intestine without perforation or abscess with bleeding
- K64.1 Second degree hemorrhoids
- K64.2 Third degree hemorrhoids
- K64.3 Fourth degree hemorrhoids
- K64.4 Residual hemorrhoidal skin tags
- K92.1 Melena
- N89.8 Other specified noninflammatory disorders of vagina
- N93.9 Abnormal uterine and vaginal bleeding, unspecified
- R04.0 Epistaxis
- R04.1 Hemorrhage from throat
- R58 Hemorrhage, not elsewhere classified
- D64.9 Anemia, unspecified
- R79.1 Abnormal coagulation profile
- H11.30 Conjunctival hemorrhage, unspecified eye
- H11.31 Conjunctival hemorrhage, right eye
- H11.32 Conjunctival hemorrhage, left eye
- H11.33 Conjunctival hemorrhage, bilateral
- H31.321 Choroidal rupture, right eye
- H31.322 Choroidal rupture, left eye
- H31.323 Choroidal rupture, bilateral
- H31.329 Choroidal rupture, unspecified eye
- N92.1 Excessive and frequent menstruation with irregular cycle
- R31.1 Benign essential microscopic hematuria
- R31.2 Other microscopic hematuria
- R31.29 Other microscopic hematuria
- N92.0 Excessive and frequent menstruation with regular cycle
- R31.21 Asymptomatic microscopic hematuria
- R31.9 Hematuria, unspecified

Procedure	Codes Description	

- CPT-4 codes
- 1960 Anesthesia for vaginal delivery only
- 1961 Anesthesia for cesarean delivery only
- 1962 Anesthesia for urgent hysterectomy following delivery
- 1963 Anesthesia for cesarean hysterectomy w/o any labor analgesia/anesthesia care
- 1967 Neuraxial labor analgesia/anesthesia, planned vaginal delivery
- 1968 Anesthesia for cesarean delivery following neuraxial labor analgesia/anesthesia
- 1969 Anes for cesarean hysterectomy following neuraxial labor analgesia/anesthesia
- 59050 Fetal monitoring in labor, physician w/written report; s & i
- 59051 Fetal monitoring in labor, physician w/written report; intrepretation only
- 59400 ROUTINE TOTAL OBSTETRIC CARE including antepartum care, vaginal delivery (with or without episiotomy, and/or forceps) and postpartum care.
- 59409 Vaginal delivery only (w/wo episiotomy &/or forceps)
- 59410 Vaginal delivery only (w/wo episiotomy &/or forceps); w/postpartum care
- 59412 Ext cephalic version, w/wo tocolysis
- 59414 Delivery of placenta (separate proc)
- 59430 Postpartum care only
- 59510 Routine obstetric care w/antepartum care, cesarean delivery, & postpartum care
- 59514 Cesarean delivery only
- 59515 Cesarean delivery only; w/postpartum care
- 59525 Subtotal/total hysterectomy after cesarean delivery
- 59610 Routine obstetric care including antepartum care, vaginal delivery (with or without episiotomy, and/or forceps) and postpartum care, after previous cesarean delivery
- 59612 Vaginal delivery only, after previous cesarean delivery (with or without episiotomy and/or forceps)
- 59614 Vaginal delivery only, previous cesarean delivery w/postpartum care
- 59618 Routine obstetric care including antepartum care, cesarean delivery, and postpartum care, following attempted vaginal delivery after previous cesarean delivery
- 59620 Cesarean delivery after failed vaginal delivery, previous cesarean delivery
- 59622 Cesarean delivery after failed vaginal delivery, previous cesarean delivery; w/postpartum care
- 99436 Attendance at delivery, at request of delivering physician, & stabilization of newborn
- 99440 Newborn resuscitation

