- 533.9 PEPTIC ULCER OF UNSPECIFIED SITE UNSPECIFIED AS ACUTE OR CHRONIC WITHOUT MENTION OF HEMORRHAGE OR PERFORATION
- 534 ACUTE GASTROJEJUNAL ULCER WITH HEMORRHAGE
- 534.2 ACUTE GASTROJEJUNAL ULCER WITH HEMORRHAGE AND PERFORATION
- 534.21 ACUTE GASTROJEJUNAL ULCER WITH HEMORRHAGE AND PERFORATION WITH OBSTRUCTION
- 534.4 CHRONIC OR UNSPECIFIED GASTROJEJUNAL ULCER WITH HEMORRHAGE
- 534.4 CHRONIC OR UNSPECIFIED GASTROJEJUNAL ULCER WITH HEMORRHAGE WITHOUT OBSTRUCTION
- 534.6 CHRONIC OR UNSPECIFIED GASTROJEJUNAL ULCER WITH HEMORRHAGE AND PERFORATION
- 534.6 CHRONIC OR UNSPECIFIED GASTROJEJUNAL ULCER WITH HEMORRHAGE AND PERFORATION WITHOUT OBSTRUCTION
- 534.9 GASTROJEJUNAL ULCER UNSPECIFIED AS ACUTE OR CHRONIC WITHOUT MENTION OF HEMORRHAGE OR PERFORATION
- 535.11 ATROPHIC GASTRITIS WITH HEMORRHAGE
- 535.31 ALCOHOLIC GASTRITIS WITH HEMORRHAGE
- 535.4 OTHER SPECIFIED GASTRITIS (WITHOUT HEMORRHAGE)
- 535.51 UNSPECIFIED GASTRITIS AND GASTRODUODENITIS WITH HEMORRHAGE
- 535.61 DUODENITIS WITH HEMORRHAGE
- 562.01 DIVERTICULITIS OF SMALL INTESTINE (WITHOUT HEMORRHAGE)
- 562.03 DIVERTICULITIS OF SMALL INTESTINE WITH HEMORRHAGE
- 562.11 DIVERTICULITIS OF COLON (WITHOUT HEMORRHAGE)
- 562.12 DIVERTICULOSIS OF COLON WITH HEMORRHAGE
- 569.85 ANGIODYSPLASIA OF INTESTINE WITH HEMORRHAGE
- 578.1 BLOOD IN STOOL
- 599.71 GROSS HEMATURIA
- 623.8 OTHER SPECIFIED NONINFLAMMATORY DISORDERS OF VAGINA
- 626.8 OTHER DISORDERS OF MENSTRUATION AND OTHER ABNORMAL BLEEDING FROM FEMALE GENITAL TRACT

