- 537.83 ANGIODYSPLASIA OF STOMACH AND DUODENUM WITH HEMORRHAGE
- 562 DIVERTICULOSIS OF SMALL INTESTINE (WITHOUT HEMORRHAGE)
- 562.02 DIVERTICULOSIS OF SMALL INTESTINE WITH HEMORRHAGE
- 562.1 DIVERTICULOSIS OF COLON (WITHOUT HEMORRHAGE)

562.13 DIVERTICULITIS OF COLON WITH HEMORRHAGE

- 569.3 HEMORRHAGE OF RECTUM AND ANUS
- 578 HEMATEMESIS
- 578.9 HEMORRHAGE OF GASTROINTESTINAL TRACT UNSPECIFIED
- 593.81 VASCULAR DISORDERS OF KIDNEY
- 599.7 HEMATURIA UNSPECIFIED
- 623.6 VAGINAL HEMATOMA
- 626.6 METRORRHAGIA
- 786.3 HEMOPTYSIS UNSPECIFIED
- 786.31 ACUTE IDIOPATHIC PULMONARY HEMORRHAGE IN INFANTS

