  - K25.5 Chronic or unspecified gastric ulcer with perforation

- K26.2 Acute duodenal ulcer with both hemorrhage and perforation
- K26.4 Chronic or unspecified duodenal ulcer with hemorrhage
- K26.6 Chronic or unspecified duodenal ulcer with both hemorrhage and perforation
- K27.4 Chronic or unspecified peptic ulcer, site unspecified, with hemorrhage
- K27.5 Chronic or unspecified peptic ulcer, site unspecified, with perforation
- K27.6 Chronic or unspecified peptic ulcer, site unspecified, with both hemorrhage and perforation
- K28.1 Acute gastroieiunal ulcer with perforation
- K28.2 Acute gastrojejunal ulcer with both hemorrhage and perforation
- K29.31 Chronic superficial gastritis with bleeding
- K29.91 Gastroduodenitis, unspecified, with bleeding
- K57.11 Diverticulosis of small intestine without perforation or abscess with bleeding
- K57.21 Diverticulitis of large intestine with perforation and abscess with bleeding
- K57.51 Diverticulosis of both small and large intestine without perforation or abscess with bleeding
- K57.53 Diverticulitis of both small and large intestine without perforation or abscess with bleeding
- K57.93 Diverticulitis of intestine, part unspecified, without perforation or abscess with bleeding
- K62.5 Hemorrhage of anus and rectum
- K64.1 Second degree hemorrhoids
- K64.3 Fourth degree hemorrhoids
- K64.9 Unspecified hemorrhoids
- K92.0 Hematemesis
- K92.1 Melena
- N89.7 Hematocolpos
- N92.1 Excessive and frequent menstruation with irregular cycle
- N93.8 Other specified abnormal uterine and vaginal bleeding
- R04.0 Epistaxis
- R31.0 Gross hematuria
- R31.9 Hematuria, unspecified
- R58 Hemorrhage, not elsewhere classified
- 185.01 Esophageal varices with bleeding
- K22.6 Gastro-esophageal laceration-hemorrhage syndrome
- K25.0 Acute gastric ulcer with hemorrhage
- K25.6 Chronic or unspecified gastric ulcer with both hemorrhage and perforation
- K26.0 Acute duodenal ulcer with hemorrhage
- K26.1 Acute duodenal ulcer with perforation
- K26.5 Chronic or unspecified duodenal ulcer with perforation
- K27.0 Acute peptic ulcer, site unspecified, with hemorrhage
- K27.1 Acute peptic ulcer, site unspecified, with perforation
- K27.2 Acute peptic ulcer, site unspecified, with both hemorrhage and perforation
- K28.0 Acute gastroieiunal ulcer with hemorrhage
- K28.4 Chronic or unspecified gastrolejunal ulcer with hemorrhage
- K28.5 Chronic or unspecified gastroleiunal ulcer with perforation

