- K28.6 Chronic or unspecified gastrojejunal ulcer with both hemorrhage and perforation
- K29.01 Acute gastritis with bleeding
- K29.21 Alcoholic gastritis with bleeding
- K29.41 Chronic atrophic gastritis with bleeding
- K29.51 Unspecified chronic gastritis with bleeding
- K29.61 Other gastritis with bleeding
- K29.71 Gastritis, unspecified, with bleeding
- K29.81 Duodenitis with bleeding
- K31.811
- Angiodysplasia of stomach and duodenum with bleeding
- K55.21 Angiodysplasia of colon with hemorrhage
- K57.01 Diverticulitis of small intestine with perforation and abscess with bleeding
- K57.31 Diverticulosis of large intestine without perforation or abscess with bleeding
- K57.41 Diverticulitis of both small and large intestine with perforation and abscess with bleeding
- K57.81 Diverticulitis of intestine, part unspecified, with perforation and abscess with bleeding
- K57.91 Diverticulosis of intestine, part unspecified, without perforation or abscess with bleeding
- K64.0 First degree hemorrhoids
- K64.2 Third degree hemorrhoids
- K64.4 Residual hemorrhoidal skin tags
- K64.5 Perianal venous thrombosis
| K64.8 | 3 | Other hemorrhoids                                   |
|-------|---|---|
| K92.2 | 2 | Gastrointestinal hemorrhage, unspecified            |
| N89.8 |   | Other specified noninflammatory disorders of vagina |
| N93.9 | ) | Abnormal uterine and vaginal bleeding, unspecified  |
| R04.1 |   | Hemorrhage from throat                              |
| R04.2 | 2 | Hemoptysis  |

Ξ.

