
535.21 - GASTRIC MUCOSAL HYPERTROPHY WITH HEMORRHAGE 535.31 - ALCOHOLIC GASTRITIS WITH HEMORRHAGE 535.40 - OTHER SPECIFIED GASTRITIS (WITHOUT HEMORRHAGE) 535.41 - OTHER SPECIFIED GASTRITIS WITH HEMORRHAGE 562.00 - DIVERTICULOSIS OF SMALL INTESTINE (WITHOUT HEMORRHAGE) 562.01 - DIVERTICULITIS OF SMALL INTESTINE (WITHOUT HEMORRHAGE) 562.03 - DIVERTICULITIS OF SMALL INTESTINE WITH HEMORRHAGE 562.11 - DIVERTICULITIS OF COLON (WITHOUT HEMORRHAGE) 562.13 - DIVERTICULITIS OF COLON WITH HEMORRHAGE 569.85 - ANGIODYSPLASIA OF INTESTINE WITH HEMORRHAGE 578.0 - HEMATEMESIS 578.1 - BLOOD IN STOOL 578.9 - HEMORRHAGE OF GASTROINTESTINAL TRACT UNSPECIFIED 593.81 - VASCULAR DISORDERS OF KIDNEY 599.70 - HEMATURIA UNSPECIFIED 599.71 - GROSS HEMATURIA 623.6 - VAGINAL HEMATOMA 626.6 - METRORRHAGIA 784.7 - FPISTAXIS 784.8 - HEMORRHAGE FROM THROAT 786.31 - ACUTE IDIOPATHIC PULMONARY HEMORRHAGE IN INFANTS 285.1 - ACUTE POSTHEMORRHAGIC ANEMIA 455.1 - INTERNAL THROMBOSED HEMORRHOIDS 455.2 - INTERNAL HEMORRHOIDS WITH OTHER COMPLICATION 455.4 - EXTERNAL THROMBOSED HEMORRHOIDS 455.5 - EXTERNAL HEMORRHOIDS WITH OTHER COMPLICATION 455.6 - UNSPECIFIED HEMORRHOIDS WITHOUT COMPLICATION 455.8 - UNSPECIFIED HEMORRHOIDS WITH OTHER COMPLICATION 455.9 - RESIDUAL HEMORRHOIDAL SKIN TAGS 456.0 - ESOPHAGEAL VARICES WITH BLEEDING 456.20 - ESOPHAGEAL VARICES IN DISEASES CLASSIFIED ELSEWHERE WITH BLEEDING 530.1 - ESOPHAGITIS 530.11 - REFLUX ESOPHAGITIS 530.12 - ACUTE ESOPHAGITIS 530.19 - OTHER ESOPHAGITIS 530.7 - GASTROESOPHAGEAL LACERATION-HEMORRHAGE SYNDROME 530.82 - ESOPHAGEAL HEMORRHAGE 531.00 - ACUTE GASTRIC ULCER WITH HEMORRHAGE WITHOUT OBSTRUCTION 531.01 - ACUTE GASTRIC ULCER WITH HEMORRHAGE WITH OBSTRUCTION 531.21 - ACUTE GASTRIC ULCER WITH HEMORRHAGE AND PERFORATION WITH OBSTRUCTION 531.40 - CHRONIC OR UNSPECIFIED GASTRIC ULCER WITH HEMORRHAGE WITHOUT OBSTRUCTION 531.41 - CHRONIC OR UNSPECIFIED GASTRIC ULCER WITH HEMORRHAGE WITH OBSTRUCTION 531.5 - CHRONIC OR UNSPECIFIED GASTRIC ULCER WITH PERFORATION 531.60 - CHRONIC OR UNSPECIFIED GASTRIC ULCER WITH HEMORRHAGE AND PERFORATION WITHOUT OBSTRUCTION 531.7 - CHRONIC GASTRIC ULCER WITHOUT MENTION OF HEMORRHAGE OR PERFORATION 532.1 - ACUTE DUODENAL ULCER WITH PERFORATION 532.21 - ACUTE DUODENAL ULCER WITH HEMORRHAGE AND PERFORATION WITH OBSTRUCTION 532.40 - CHRONIC OR UNSPECIFIED DUODENAL ULCER WITH HEMORRHAGE WITHOUT OBSTRUCTION

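### Both ICD-10 bleeding lists omit non-perforated diverticulitis with bleeding of the small intestine (K57.13) and of the large intestine (K57.33), although both ICD-9 lists count diverticulitis with hemorrhage at these sites

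*Combined protocol and SAP*

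**What the plan says.** Section 6.3.1 defines the primary outcome as major plus clinically relevant non-major (CRNM) bleeding through 365 days. Appendix A sends the reader to the Major Bleeding and CRNM Bleeds sheets for the codes. It uses the same two sheets for the active-bleeding exclusion over [-180, 0].

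ICD-9, Major Bleeding sheet (the group that also needs a transfusion code): "562.03 DIVERTICULITIS OF SMALL INTESTINE WITH HEMORRHAGE" and "562.13 DIVERTICULITIS OF COLON WITH HEMORRHAGE".

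ICD-9, CRNM Bleeds sheet: "562.03 - DIVERTICULITIS OF SMALL INTESTINE WITH HEMORRHAGE" and "562.13 - DIVERTICULITIS OF COLON WITH HEMORRHAGE".

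ICD-10, both sheets: for the small and the large intestine without perforation, the entries are diverticulosis only, "K57.11 Diverticulosis of small intestine without perforation or abscess with bleeding" and "K57.31 Diverticulosis of large intestine without perforation or abscess with bleeding". For both sites together and for an unspecified site, the diverticulitis codes are listed as well: "K57.53 Diverticulitis of both small and large intestine without perforation or abscess with bleeding" and "K57.93 Diverticulitis of intestine, part unspecified, without perforation or abscess with bleeding".

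K57.13 and K57.33 appear nowhere in the document, and no reason is given for leaving them out.

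**The concern.** The same kind of admission is treated differently according to the coding system in use. An inpatient bleed coded as colonic diverticulitis with hemorrhage qualifies on that code alone under ICD-9. Under ICD-10, without perforation or abscess, it does not. The ICD-10 lists are also inconsistent within themselves: they accept the non-perforated diverticulitis bleed when the site is unspecified or covers both intestines, and reject it when one site is named.

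Two things are at stake. Some true bleeds would not count as primary events. Some patients with a recent bleed would pass the bleeding exclusion.

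**Working it through.** **1. The lists side by side.** The entries below are the same on the Major Bleeding and CRNM Bleeds sheets.

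| Site | ICD-9 diverticulitis with hemorrhage | ICD-10 diverticulosis, bleeding, not perforated | ICD-10 diverticulitis, bleeding, not perforated | ICD-10 diverticulitis, bleeding, perforated |
|---|---|---|---|---|
| Small | 562.03 | K57.11 | absent (K57.13) | K57.01 |
| Large | 562.13 | K57.31 | absent (K57.33) | K57.21 |
| Both | none listed | K57.51 | K57.53 | K57.41 |
| Unspecified | none listed | K57.91 | K57.93 | K57.81 |

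Each ICD-10 sheet has ten K57 bleeding codes, and the two sets are identical. The pattern in the table has 3 × 4 = 12 cells, so the gap is 12 − 10 = 2 codes. The meaning of K57.13 and K57.33 is read from that pattern (.x1 diverticulosis, .x3 diverticulitis).

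**2. Is it a reading error from the PDF?** The K57 codes run in a different order on the two sheets, yet the same two are absent from both. Accidental loss of the same two lines from two differently ordered lists is implausible.

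**3. Who is exposed.** The documents give no date for the coding change. I assume late 2015 and count entry years 2016 to 2020 in the pooled columns of the Appendix B tables.

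- Matched rivaroxaban: 39,809 + 45,194 + 10,679 + 9,185 + 2,733 = 107,600; 107,600 / 184,107 = 58.4%.
- Matched apixaban: 39,772 + 45,182 + 10,723 + 9,103 + 2,699 = 107,479; 107,479 / 184,107 = 58.4%.
- Unmatched rivaroxaban: 40,037 + 45,661 + 10,686 + 9,185 + 2,733 = 108,302; 108,302 / 230,439 = 47.0%.
- Unmatched apixaban: 71,719 + 74,915 + 24,376 + 27,560 + 9,375 = 207,945; 207,945 / 298,310 = 69.7%.

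These are shares of patients to whom the ICD-10 lists apply, not shares who lose an event. Some 2015 entrants would also be followed past the change, so 58% is not an upper limit on exposure.

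**4. Effect on power.** Section 10 is reproduced first. Events = matched N × risk / 1,000, and power = Φ(√(events)/2 × |ln 0.8| − 1.96).

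- Optum: 68,134 × 19.8838767 / 1,000 = 1,354.77 events; power 0.9841, as stated.
- MarketScan: 61,846 × 28.0384028 / 1,000 = 1,734.06 events; power 0.9964, as stated.
- Pooled: 368,214 × 41.4155034 / 1,000 = 15,249.77 events; power 1, as stated.
- CMS: 238,234 × 52.5732835 / 1,000 = 12,524.74 events; power 1, as stated.

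No event counts by code are given, so the loss below is an assumed range.

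| Assumed event loss | Optum power, HR 0.8 | MarketScan power, HR 0.8 | Pooled and CMS |
|---|---|---|---|
| 0.5% | 0.9837 | 0.9963 | 1 |
| 5% | 0.9795 | 0.9949 | 1 |

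**The case against.** **Much of the condition is still captured.** Perforated, both-site and unspecified-site forms are listed (K57.01, .21, .41, .53, .81, .93). A reader might infer that the ICD-10 lists miss diverticulitis bleeding altogether; they do not. The gap is the non-perforated, single-site form. Any inpatient diagnosis position counts, and CRNM bleeding needs no transfusion code. Many of these admissions would therefore qualify through K92.2, K62.5, D62 or, on the CRNM sheet, unspecified anemia (D64.9). This stands and limits the size of the point.

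**The comparison is hardly touched.** With calendar year balanced after matching, the loss should be similar in the two arms. This also stands. A reader might infer a biased hazard ratio from the 47.0% against 69.7% split before matching. That split concerns only the crude row of Table 4, not the matched estimate.

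**The lists may follow an earlier algorithm.** A study in Medicare beneficiaries is cited beside the outcome definition, and its code list may have the same gap. The documents do not say so. Inheritance would explain the omission without making the lists consistent.

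**The coding eras differ in other ways.** The ICD-9 sheets also count diverticular disease and gastritis stated to be without hemorrhage, such as 562.11, with no non-bleeding K57 or K29 counterpart in ICD-10. Two added codes will not make the eras equivalent. That is true, but it does not close this gap: K57.13 and K57.33 are bleeding codes of the kind the ICD-10 lists otherwise include.

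**Conclusion.** The omission is real and confirmed in both ICD-10 lists. As written, the plan misses some diverticulitis bleeds in the ICD-10 period that it counts under ICD-9, both as primary events and as grounds for exclusion. This is a minor defect of outcome and eligibility measurement. The number of events lost cannot be computed from the documents, and nothing in them supports calling it large.

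The 58% exposure figure depends on the assumed late-2015 coding change. The expectation of little arm bias rests on the balance of calendar year after matching. Even an assumed 5% loss of events leaves power at HR 0.8 at 0.9795 or higher in every database.

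**What to change.** Before the comparative analysis of Section 13, which carries no date yet, add K57.13 and K57.33 to the ICD-10 part of the Major Bleeding sheet (in the group that requires transfusion) and of the CRNM Bleeds sheet. Apply the change to both the outcome and the [-180, 0] exclusion.

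The edit is two codes in two lists, but it is not free. Eligibility changes, so the cohort flow (Section 5.3), feasibility and event counts (Section 7), matching and balance (Section 9, Appendix B) and power tables (Sections 8 and 10) need re-running. That cost is small while no treatment effect has been estimated.

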#### ICD-9 procedure

codes

- 72.xx Forceps, vacuum, & breech 73.xx Other including manual delivery 74xx Cesarean section 75.4x Manual removal of placenta ICD-10 procedure codes Normal Delivery 10E0X22 Delivery of Products of Conception, External Approach C-Section 10D0020 Extraction of Products of Conception, High, Open Approach 10D0021 Extraction of Products of Conception, Low, Open Approach Extraction of Products of Conception, Extraperitoneal, Open Approach 10D0022 Other assisted delivery (forceps, vacuum, internal version, other) 10D0723 Extraction of Products of Conception, Low Forceps, Via Natural or Artificial Opening 10D0724 Extraction of Products of Conception, Mid Forceps, Via Natural or Artificial Opening 10D0725 Extraction of Products of Conception, High Forceps, Via Natural or Artificial Opening 10D0726 Extraction of Products of Conception, Vacuum, Via Natural or Artificial Opening 10D0727 Extraction of Products of Conception, Internal Version, Via Natural or Artificial Opening 10D0728
  - Extraction of Products of Conception, Other, Via Natural or Artificial Opening

ICD-9 code	Definition	Gestational A	ge
		Weeks	Days
765.21	Less than 24 c	:24	168
765.22	24 completed	weeks of gest	ation
765.23	25-26 comple	26	182
765.24	27-28 comple	28	196
765.25	29-30 comple	30	210
765.26	31-32 comple	32	224
765.27	33-34 comple	34	238
765.28	35-36 comple	36	252

ICD-10 code Definition Gestational Age

•

I

		Weeks	Days
P07.21	Extreme imm	23	161
P07.22	Extreme imm	23	161
P07.23	Extreme imm	24	168
P07.24	Extreme imm	25	175
P07.25	Extreme imm	26	182
P07.26	Extreme imm	27	189
P07.31	Preterm new	28	196
P07.32	Preterm new	29	203
P07.33	Preterm new	30	210
P07.34	Preterm new	31	217
P07.35	Preterm new	32	224
P07.36	Preterm new	33	231
P07.37	Preterm new	34	238
		25	245
P07.38	Preterm new	35	245
P07.38 P07.39	Preterm new Preterm new		245 252
	Preterm new	36	
P07.39	Preterm new	36	252
P07.39 Codes indicating	Preterm new extreme prem	36 naturity	252
P07.39 Codes indicating	Preterm new extreme prem	36 naturity Gestational A Weeks	252 ge
P07.39 Codes indicating ICD-9 code	Preterm new extreme prem Definition Disorders rela	36 naturity Gestational A Weeks	252 ge Days 196
P07.39 Codes indicating ICD-9 code 765.0	Preterm new extreme prem Definition Disorders rela Extreme imm	36 naturity Gestational A Weeks 128	252 ge Days 196 cified [weight
P07.39 Codes indicating ICD-9 code 765.0 765.00	Preterm new extreme prem Definition Disorders rela Extreme imm Extreme imm	36 Gestational A Weeks 128 aturity, unspe	252 Days 196 cified [weight an 500 grams
P07.39 Codes indicating ICD-9 code 765.0 765.00 765.01	Preterm new extreme prem Definition Disorders rela Extreme imm Extreme imm Extreme imm	36 Gestational A Weeks 128 aturity, unspe- aturity, less tha	252 Days 196 cified [weight an 500 grams 9 grams
P07.39 Codes indicating ICD-9 code 765.0 765.00 765.01 765.02	Preterm new extreme prem Definition Disorders rela Extreme imm Extreme imm Extreme imm Extreme imm	36 aturity Gestational A Weeks 28 aturity, unspe- aturity, less tha aturity, 500-74	ge Days 196 cified [weight an 500 grams 9 grams 9 grams
P07.39 Codes indicating ICD-9 code 765.0 765.00 765.01 765.02 765.03	Preterm new extreme prem Definition Disorders rela Extreme imm Extreme imm Extreme imm Extreme imm Extreme imm	36 aturity Gestational A Weeks 128 aturity, unspe- aturity, less tha aturity, 500-74 aturity, 750-99	ge Days 196 cified [weight an 500 grams 9 grams 9 grams 1,249 grams
P07.39 Codes indicating ICD-9 code 765.0 765.00 765.01 765.02 765.03 765.03 765.04	Preterm new extreme prem Definition Disorders rela Extreme imm Extreme imm Extreme imm Extreme imm Extreme imm Extreme imm	36 aaturity Gestational A Weeks 128 aturity, unspe aturity, less tha aturity, 500-74 aturity, 750-99 aturity, 1,000-1	252 Days 196 cified [weight an 500 grams 9 grams 9 grams 1,249 grams 1,499 grams
P07.39 Codes indicating ICD-9 code 765.00 765.01 765.02 765.03 765.04 765.04 765.05	Preterm new extreme prem Definition Disorders rela Extreme imm Extreme imm Extreme imm Extreme imm Extreme imm Extreme imm Extreme imm	36 aaturity Gestational A Weeks 128 aturity, unspe aturity, less tha aturity, 500-74 aturity, 750-99 aturity, 1,000-1 aturity, 1,250-1	ge Days 196 cified [weight an 500 grams 9 grams 1,249 grams 1,499 grams 1,749 grams
P07.39 Codes indicating ICD-9 code 765.00 765.01 765.02 765.02 765.03 765.04 765.05 765.06	Preterm new extreme prem Definition Disorders rela Extreme imm Extreme imm Extreme imm Extreme imm Extreme imm Extreme imm Extreme imm Extreme imm	36 Gestational A Weeks 128 aturity, unspe aturity, less tha aturity, 500-74 aturity, 750-99 aturity, 1,000-1 aturity, 1,250-1 aturity, 1,500-1	ge Days 196 cified [weight an 500 grams 9 grams 9 grams 1,249 grams 1,499 grams 1,749 grams 1,749 grams

	2011111011	e o o ta ti o ti a ti o	
		Weeks	Days
P07.2	Extreme imm	28	196
P07.20	Extreme imm	aturity of newb	porn, unspecified weeks of gestation
O42.012	Preterm prem	ature rupture	of membranes, onset of labor within 24 hours of rupture, second trimester

Other preterm

codes				
ICD-9 code	Definition	Gestationa	l Age	
		Weeks	Days	
765.1	Disorders re	la 35	245	
765.10	Other prete	rm infants, u	nspecified [weigh	nt]
765.11	Other preter	m infants, les	s than 500 gram	S
765.12	Other prete	rm infants, 5	00-749 grams	
765.13	Other prete	rm infants, 7	50-999 grams	
765.14	Other preter	m infants, 1,0	00-1,249 grams	
765.15	Other preter	m infants, 1,	250-1,499 grams	
765.16	Other preter	m infants, 1,	00-1,749 grams	
765.17	Other preter	m infants, 1,	50-1,999 grams	
765.18	Other preter	m infants, 2,0	00-2,499 grams	
644.21	Onset of de	livery before	37 completed we	eks of gestation
ICD-10 code	Definition	Gestationa	l Age	
		Weeks	Days	

	WEEKS	Days
P05.01	Disorders of n 35	245
P05.02	Disorders of newborn relate	d to slow fetal growth and fetal malnutrition, 500-749 grams
P05.03	Disorders of newborn relate	d to slow fetal growth and fetal malnutrition, 750-999 grams
P05.04	Disorders of newborn relate	d to slow fetal growth and fetal malnutrition, 1000-1249 grams
P05.05	Disorders of newborn relate	d to slow fetal growth and fetal malnutrition, 1250-1499 grams
P05.06	Disorders of newborn relate	d to slow fetal growth and fetal malnutrition, 1500-1749 grams
P05.07	Disorders of newborn relate	d to slow fetal growth and fetal malnutrition, 1750-1999 grams
P05.11	Newborn small for gestationa	al age, less than 500 grams

P05.12 P05.13 Newborn small for gestational age, 500-749 grams

Newborn small for gestational age, 750-999 grams

P05.14 Newborn small for gestational age, 1000-1249 grams

- P05.15 Newborn small for gestational age, 1250-1499 grams P05.16
- Newborn small for gestational age, 1500-1749 grams Newborn small for gestational age, 1750-1999 grams
- P05.17
- P07.0 Extremely low birth weight newborn P07.00
- Extremely low birth weight newborn, unspecified weight P07.01 Extremely low birth weight newborn, less than 500 grams
- P07.02 Extremely low birth weight newborn, 500-749 grams
- P07.03 Extremely low birth weight newborn, 750-999 grams
- P07.1 Other low birth weight newborn
- P07.10 Other low birth weight newborn, unspecified weight
- P07.14 Other low birth weight newborn,1000-1249 grams
- P07.15 Other low birth weight newborn, 1250-1499 grams
- P07.16 Other low birth weight newborn, 1500-1749 grams
- P07.17 Other low birth weight newborn, 1750-1999 grams
- P07.3 Preterm [premature] newborn [other]
- P07.30 Preterm newborn, unspecified weeks of gestation
- 060.1 Preterm labor with preterm delivery
- O42.01 Preterm premature rupture of membranes, onset of labor within 24 hours of rupture
- 042.019 Preterm premature rupture of membranes, onset of labor within 24 hours of rupture, unspecified trimester
- 042.013 Preterm premature rupture of membranes, onset of labor within 24 hours of rupture, third trimester
- 644.2 early onset of delivery
- 644.20 Early onset of delivery, unspecified as to episode of care or not applicable
- 644.21 Early onset of delivery, delivered, with or without mention of antepartum condition
- 776.6 anemia of prematurity
- 362.20 retinopathy of prematurity, unspecified
- 362.22 retinopathy of prematurity, stage 0
- 362.23 retinopathy of prematurity, stage 1
- 362.24 retinopathy of prematurity, stage 2
- 362.25 retinopathy of prematurity, stage 3
- 362.26 retinopathy of prematurity, stage 4 362 27 retinopathy of prematurity, stage 5
- CPT
- 49491 repair, initial inguinal hernia, preterm infant (younger than 37 weeks gestation at birth), performed from birth up to 50 weeks postconception
- 49492 repair, initial inguinal hernia, preterm infant (younger than 37 weeks gestation at birth), performed from birth up to 50 weeks postconception
- 67229 treatment of extensive or progressive retinopathy, 1 or more sessions; preterm infant (less than 37 weeks gestation at birth), performed from
- 836 anesthesia for hernia repairs in the lower abdomen not otherwise specified, infants younger than 37 weeks gestational age at birth

